11.2 Medical History

The medical history will be summarized from the “Medical History” eCRF page, using MedDRA, version 22.0 (or above), preferred term as event category and system organ class (SOC) body term as Body System category.

Medical conditions will be summarized by SOC and preferred term, providing the number and percentage of subjects with the condition, as well as the number and percentage of conditions. Summaries will be presented two-fold, ordered alphabetically for SOC, and PT within SOC.

If required for an analysis, incomplete date fields will be imputed as follows:

- Missing start day and month will default to the first day of the month and first month of the year, subject to the following exceptions:
 - Missing start day and month for medical history stopped prior to IMP administration will not be imputed.
- Missing stop day and month will default to the last day of the month and last month of the year, subject to the following exceptions:

- If stop day is missing for a known medical history, then the stop day will default to 1 day prior the IMP start day.
- If stop day and month is missing for a known medical history, then the stop month and day will default to 1 day prior to IMP start date.
- Missing years will not be imputed.

12 Previous or Concomitant Medications/Procedures

Previous medications are medications, other than trial medications and pre-medications for trial drug, which are taken within four weeks prior to first IMP administration and for which the end date of the medication < date of “study day 1”.

Previous treatment will be summarized from the “Concomitant Medications” eCRF page. Anatomical Therapeutic Chemical (ATC) term 2nd level and preferred term will be tabulated as given from the WHODrug Global Version is March 2019 (or above) and format is B3. In case multiple ATC’s are assigned to a drug, all ATC-2nd level will be used for reporting.

Concomitant treatments are medications, other than trial medications, which are taken by subjects any time on-trial (the end date of the medication \geq date of “study day 1”, or medication that is ongoing with a start date \geq date of “study day 1”).

Concomitant treatment will be summarized from the “Concomitant Medications” eCRF. ATC-2nd level and preferred term will be tabulated as given from WHODrug Global Version is March 2019 (or above) and format is B3. In case multiple ATC’s are assigned to a drug, all ATC-2nd level will be used for reporting.

Prohibited medications are medications, other than trial medications, listed in section 6.5.3 of the trial protocol that are taken by subjects at any time.

- Prohibited prior medications will be summarized from the “Prior Drug History” eCRF page. ATC level 2 and preferred term will be tabulated as given from the WHODrug Global Version is March 2019 (or above) and format is B3. In case multiple ATC’s are assigned to a drug, all ATC-2nd level will be used for reporting.
- Prohibited concomitant medications, which includes medications that were started prior to dosing but were not stopped prior to dosing, will be summarised and listed separately. Prohibited concomitant medications will be identified from the “Concomitant Medications” eCRF page, using Appendix B as guide. ATC level 2 and preferred term will be tabulated as given from the WHODrug Global Version is March 2019 (or above) and format is B3. In case multiple ATC’s are assigned to a drug, all ATC-2nd level will be used for reporting.

All **Concomitant Procedures**, which were undertaken any time on trial, will be listed according to the eCRF page “Concomitant Procedure”.

- Concurrent procedures will be listed by verbatim term.

If required for an analysis, incomplete date fields will be imputed as follows:

- Missing start day and month will default to the first day of the month and first month of the year, subject to the following exceptions:

- If concomitant medication start day is missing and month and year is the same as the month and year of IMP administration, then the start day will default to the IMP start day. If the month or year are different, the start day will default to the first day of the month.
- If start day and month is missing and year is the same as the year of IMP administration and stop date is not missing stop date, then the start day and month will default to the IMP start day and month. If the year is different, then the start day=01 and month=Jan.
- Missing stop dates will default to the last day of the month and last month of the year, subject to the following exceptions:
 - If stop day is missing for a known previous medication, then the stop day will default to 1 day prior the IMP start day.
 - If stop day and month is missing for a known prior medication, then the stop month and day will default to 1 day prior to IMP start date.
 - If the stop day and month for a concomitant medication is missing, it will default to the day and month of last contact with the participant.
- Missing years will not be imputed.

Note: ATC coding will not be indication/other differentiators (namely route) based, but all ATC available for a drug in the dictionary will be provided.

13 Treatment Compliance and Exposure

Compliance and exposure will be reported for the SAF, mITT and PP analysis sets.

All dosing calculations and summaries will be based on “Dosing Preparation” CRFs pages.

Compliance will be derived as follows:

- $100 \times \{\text{Actual number of doses administered} / \text{expected number of doses that were to be administered}\}$, rounded to the nearest integer using the ROUND() function.

Compliance will be categorised as:

- Compliance = 0% {0 dose administered in C1-C4}
- Compliance = 100% {1 dose administered in C1-C4}

Compliance will be summarised by cohort and compliance level, as well as listed by cohort and subject.

Exposure, in terms of dosing, will be derived as follows:

- Exposure:

{Actual Dose [mg]}

If *Actual Dose* is missing, exposure will be kept as missing.

- Exposure with respect to baseline weight:

{Actual Dose [mg]} / weight [kg], as calculated using the weight measurement at baseline

If *Actual Dose* is missing, exposure will be kept as missing.

14 Efficacy Analyses

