## **6.5 Concomitant Therapy**

All concomitant therapies (e.g., medicines or nondrug interventions) used from the time participant's parent or guardian/legally authorized representative signs the ICF until completion of the study, including any changes, will be recorded in the appropriate eCRF. For prescription and over-the-counter medicines, vaccines, vitamins, and herbal supplements, the name, reason for use, dates administered, and dosing information will be recorded. All concomitant medications (within 7 days of participant's study treatment) received by nursing mothers of enrolled participants will be recorded on the appropriate eCRF.

Contact the Medical Monitor for any questions on concomitant or prior therapy.

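### SAP Section 12 places a non-prohibited drug started before Day 1 and recorded as ongoing in neither the previous nor the concomitant medication table

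*SAP*

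**What the plan says.** SAP Section 12 (Previous or Concomitant Medications/Procedures) sorts medications by date into two summaries.

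- **Previous:** medications "which are taken within four weeks prior to first IMP administration and for which the end date of the medication" is earlier than study Day 1.
- **Concomitant:** medications "which are taken by subjects any time on-trial (the end date of the medication" is on or after study Day 1, "or medication that is ongoing with a start date" on or after study Day 1).

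The same section then describes a separate output for prohibited drugs taken concomitantly, "which includes medications that were started prior to dosing but were not stopped prior to dosing, will be summarised and listed separately".

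Its rules for incomplete dates include: "If the stop day and month for a concomitant medication is missing, it will default to the day and month of last contact". They close with: "Missing years will not be imputed".

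On collection, protocol Section 6.5 is broad: "All concomitant therapies (e.g., medicines or nondrug interventions) used from the time" of consent until the end of the study are to be recorded in the eCRF.

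**The concern.** The two definitions should between them cover every drug taken in the four weeks before dosing or at any time after it. They do not. A drug the child was already taking before Day 1, and which is still open when recording closes, has no end date to test and a start date that fails the ongoing condition.

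The opening words of the concomitant definition would include such a drug, because it was taken on trial. The bracketed rule, which is what a programmer would code, excludes it. Within one section, concomitant therefore has two meanings: an inclusive one for prohibited drugs and a narrower one for all others.

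At stake is the completeness of a descriptive table. The data are collected under the protocol but would not appear in either summary.

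**Working it through.** There is no figure in the plan to reproduce. The check applies the written rules to a set of date patterns.

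**Rules, from SAP Section 12**

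- P (previous): an end date exists and falls before Day 1. The four-week condition was coded as an end date no earlier than Day -28. That choice does not affect the result, since P needs an end date in any case.
- C1 (concomitant, first branch): an end date exists and is on or after Day 1, whatever the start date.
- C2 (concomitant, second branch): recorded as ongoing, and the start date is on or after Day 1.
- Concomitant = C1 or C2.
- Revised rule: concomitant = C1 or ongoing, with no start-date condition.

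**Results**

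| Start | End | Previous | Concomitant as written | Concomitant, revised |
|---|---|---|---|---|
| Day -10 | Day -3 | yes | no | no |
| Day -10 | Day 1 | no | yes | yes |
| Day -10 | Day 5 | no | yes | yes |
| Day -10 | ongoing | **no** | **no** | yes |
| Day -1 | ongoing | **no** | **no** | yes |
| Day 1 | ongoing | no | yes | yes |
| Day 3 | Day 6 | no | yes | yes |
| Day 3 | ongoing | no | yes | yes |

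As written, six of the eight patterns are classified exactly once and two fall in neither table. Both are drugs started before Day 1 and ongoing. Under the revised rule all eight are classified exactly once, and only those two change.

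**Do the date rules close the gap?** If the missing end date were first set to last contact (Day 21, say), C1 would be met and the drug would be concomitant. The SAP does not get there:

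1. The last-contact rule is written for a drug that is already concomitant, which is the point to be decided.
2. That rule fills in a day and month. An ongoing record has no stop year either, and years are not imputed.
3. The general default for stop dates (end of month, end of year) also needs a year.

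**Comparison within the section.** The prohibited-drug output expressly takes in "medications that were started prior to dosing but were not stopped prior to dosing". That is the class the general definition leaves out.

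**The case against.** The strongest reply is that this is a drafting slip and the intent is plain. The lead-in covers anything taken on trial, the bracket can be read as illustration, and the prohibited-drug wording can be read as clarifying what concomitant means throughout. A careful programmer might well include these records. That is fair as to intent, but the bracket is the only operational rule given for the general table, and followed literally it produces an incomplete one.

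The reply is right on scope. A reader might infer that co-medication on board at dosing is lost in general. The documents do not support this: the first branch captures any drug that stopped on or after Day 1, however early it started.

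A reader might also infer that the drugs that matter for pharmacokinetics go unseen. That is not supported either. The drugs the protocol names as altering praziquantel levels are in protocol Section 6.5.3, and SAP Section 12 defines prohibited medications by that section, so they are captured when started before dosing and not stopped. SAP Appendix B adds broad classes, including all systemic anti-infectives, and SAP Section 8.2 bars takers of prohibited medication from the PK population.

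The affected class is also likely to be small. Protocol Section 5.2 excludes children with acute illness in the 7 days before screening or with debilitating illness. Section 6.5.3 requires investigator approval for any medication from screening onward, apart from occasional paracetamol or ibuprofen.

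**Conclusion.** The gap is real and narrow. As SAP Section 12 is worded, a non-prohibited medication started before study Day 1 and recorded as ongoing with no end date appears in neither the previous nor the concomitant table. The finding assumes that the bracketed dates are what is programmed and that ongoing drugs are recorded without an end date.

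The number of children affected cannot be derived from the documents. To say that every record in the class is missed is true but uninformative, since the class is defined by what the rule misses.

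The effect stops at the descriptive medication tables. The cure-rate and egg-reduction analyses and the adverse event tables do not use this classification. Per-protocol exclusions for medication rest on the prohibited-drug route, which is intact. The records themselves remain in the eCRF. This is a minor correction of wording, and it leaves the trial's conclusions untouched.

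**What to change.** In SAP Section 12, redefine concomitant treatment as a medication, other than trial medication, whose end date is on or after study Day 1, or which is ongoing irrespective of its start date. Leave the previous-medication definition as it is. The prohibited concomitant output already uses the inclusive rule and needs no change.

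The cost is one line of SAP text and one programming condition, with no new data collection.

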14.1 Primary Endpoint Analyses

14.1.1 Primary Analyses of Clinical Cure Rate

| Analysis (Analysis Population) | Derivation | Statistical Analysis Methods | Missing data handling |
|---|--|--|---|
| Primary endpoint: Cure rate 17 to 21 days after treatment, in children 4 to 6 years of age infected with S. mansoni (Treatment group 1a and 1b) | | | |
| Primary (mITT) | 
Clinical cure is defined as no parasite eggs in the stool 17 to 21 days after treatment.
 
Egg counts will be determined by the Kato-Katz method: One stool sample will be collected during the pre screening period (Day -28 to Day -1) and the second one within a maximum of 5 days thereafter as baseline. Two additional stool samples will be collected between Day 17 to 21 after dosing to determine efficacy: the first one will be collected within the 17 to 21 day window and the second one within a maximum of 5 days following collection of the 1st sample. Three Kato-Katz thick smears (41.7 mg) will be prepared from each stool sample
 | 
No hypothesis testing will be performed. Point estimates and corresponding two-sided 95% CIs will be determined.
 
Subjects cured of infection during the trial will be labelled as "responders". Responders will be defined as subjects with no parasite eggs (as determined by Kato-Katz method) in the End of Study stool samples, 17 to 21 days after treatment, according to the eCRF page "End of Study (Day 17 to Day 21)". Responders and non-responders will be coded as follows:
 
 For responders, response = 1 For non-responders, response = 0 
The proportion of responders in each cohort will be determined based on a binomial distribution. Exact 95% CIs will be calculated based on the Clopper-Pearson method. The PROC FREQ procedure in SAS will be used with the BINOMIAL and EXACT option for point estimates and corresponding 95% CIs.
 
Point estimates and corresponding 95% CIs will be presented for cure rate, in terms of proportion of responders, by cohort. Response will be listed by cohort and subject. Estimates of cure rate will be presented graphically in the form of forest plots presenting point estimates and 95% CIs.
 
For mITT analysis tables will be presented with imputation and without imputation.
 
Results will be presented for each analysis set.
 | 
If the End of Study Kato-Katz egg count is missing, it will be imputed using the Last Observation Carried Forward (LOCF) approach. Subjects with missing data will be considered non-responders.
 |
| Sensitive (PP) | | | No imputation will be done |
| Sensitive (SAF) | | | No imputation will be done |

14.2 Secondary Endpoint Analyses

| Analysis (Analysis Population) | Derivation | Statistical Analysis Methods | Missing data handling |
|--------------------------------------|------------|------------------------------|-----------------------|
| CONFIDENTIAL INFORMATION | | | |

| Secondary endpoint: Cure rate 17 to 21 days after treatment, in children 2 to 3 years of age and in infants/toddlers 3 to < 24 months of age infected with S. mansoni (Cohorts 2 and 3, respectively) | | | |
|--|--|---|---|
| Primary (mITT) See 14.2.1 for details about analysis for participant 3 to 24 months of age (Cohort 3). | Same as Cohort 1 (primary analysis). | Same as Cohort 1 (primary analysis). | If the End of Study Kato-Katz egg count is missing, it will be imputed using the Last Observation Carried Forward (LOCF) approach. Subjects with missing data will be considered non-responders. |
| Primary (PP) | | | No Imputation will be done. |
| Secondary endpoint: Cure rate 17 to 21 days and 35 to 40 days after treatment, in children 3 months to 6 years of age infected with S. haematobium (Cohort 4) | | | |
| Primary (mITT) | 
At each assessment visit after treatment, clinical cure is defined as no parasite eggs in the urine samples.
 
Egg counts will be determined by urine examination using the urine filtration technique: The first sample will be collected during the pre screening period (Day -28 to Day -1) and the second and the third one within a maximum of 5 days thereafter as baseline. At the End-of-Study visit (between Day 17 and 21) Cohort 4 participants will be asked to provide three urine samples (about 10 mL each): the first one will be collected within the 17 to 21-day window and the other two within a maximum of 5 days following collection of the 1st sample, for analysis by the filtration method.
 
Similarly, at the Extended Follow-up
 | 
No hypothesis testing will be performed. Point estimates and corresponding two-sided 95% CIs will be determined.
 
Subjects cured of infection during the trial will be labelled as "responders". At each of the End of Study visit (17 to 21 days after treatment, according to the eCRF page "End of Study (Day 17 to Day 21)") and the Extended Follow-up visit (35 to 40 days after treatment, according to the eCRF page "Extended Follow-up (Day 35 to Day 40)"), responders will be defined as subjects with no parasite eggs urine samples, (as determined by urine filtration method)
 
Responders and non-responders will be coded as follows:
 
 For responders, response = 1 For non-responders, response = 0 
The proportion of responders in each cohort will be determined based on a binomial distribution. Exact 95% CIs will be calculated based on the Clopper-Pearson method. The PROC FREQ procedure in SAS will be used with the appropriate BINOMIAL and EXACT statements for point estimates and corresponding 95% CIs.
 
Point estimates and corresponding 95% CIs will be presented for cure rate, in terms of proportion of responders, by cohort. Response will be listed by cohort and subject. Estimates of cure rate will be presented graphically in the form of forest plots presenting point estimates and 95% CIs.
 
Results will be presented for each analysis set.
 | 
If the End of Study or Extended Follow-up visit egg count is missing, carried forward for imputation. According to this rule subjects with missing egg count data at post-treatment assessment will be considered as non-responders at the End-of-study visit. For cohort 4b, if the assessment at Extended Follow-up visit is missing, the assessment result at End-of-study visit will be carried forward.
 |

| | | | |
|---|---|---|---|
| | 
visit, Cohort 4 participants will be asked to provide three additional urine samples (about 10 mL each) on different days between Day 35 and Day 40. Each urine samples will be filtered through a filter mesh. This mesh is then examined under the microscope for S. haematobium egg count.
 | | |
| 
Secondary endpoint: Egg Reduction Rate (ERR) 17 to 21 days after treatment, in children 4 to 6 years of age infected with S. mansoni (Treatment group 1a and 1b)
 | | | |
| 
Primary (mITT)
 | 
ERR from pre treatment to 17 to 21 days after treatment, using parasite egg counts as determined by the Kato-Katz method for Cohort 1.
 | 
The group/collective egg reduction rate will be determined for cohort 1a and 1b as follows:
 
Step 1: Calculate the arithmetic group mean and geometric group mean egg counts (egp) at each visit. The geometric mean is defined as:
 $GM(x_1, \dots, x_n) = e^{(1/n \sum_{i=1}^n \log(x_i+1))} - 1$ 
Where x_i is the egg count for subject i.
 
Step 2: Calculate group ERR for each treatment group and individual ERR
 
 • $ERR_A \text{ (%) } = \text{relative difference expressed in percent between the post-treatment mean egg count and the pre-treatment mean egg count } ((\text{pre-treatment mean egg count} - \text{post-treatment mean egg count}) / \text{pre-treatment egg count})$. • $ERR_G \text{ (%) } = \text{relative difference expressed in percent between the geometric mean post-treatment egg count and geometric mean pre-treatment egg count } ((\text{geometric mean pre-treatment egg count} - \log\text{-transformed post-treatment egg count}) / \text{geometric mean pre-treatment egg count})$. 
In addition: individual ERR (iERR) will be calculated for each patient:
 
 • $iERR \text{ (%) } = \text{relative difference expressed in percent between the post-treatment egg count and the pre-treatment egg count } ((\text{pre-treatment egg count} - \text{post-treatment egg count}) / \text{pre-treatment egg count})$. 
All raw egg counts will be multiplied by 4 in background of EDC system generating egg counts as eggs/gram (mansoni) and eggs/10ml (haematobium) respectively.
 | 
If the End of Study Kato-Katz egg count is missing, it will be imputed using the Last Observation Carried Forward (LOCF) approach. Subjects with missing data will be considered non-responders.
 |
| 
Primary (PP)
 | | | 
No Imputation will be done.
 |

| | | | |
|--|---|---|--|
| | | 
Point and interval estimates of ERR_A, ERR_G and proportion of individuals with $iERR \geq 90\%$ will be presented by treatment group. 95% CIs of these 3 parameters will be calculated by bootstrapping (using SAS procedure SURVEYSELECT). Mean Kato-Katz egg counts will be listed by cohort and subject and time point. Estimates of ERR_A, ERR_G and $iERR$ will be presented graphically in the form of boxplots, by cohort.
 
Results will be presented for each analysis set.
 | |
| Secondary endpoint: Egg Reduction Rate (ERR) in children 2 to 3 years of age and in infants and toddlers 3 months to < 24 months of age infected with S. mansoni (Cohorts 2 and 3, respectively) and in children 3 months to 6 years of age infected with S. haematobium (Cohort 4). | | | |
| Primary (mITT) See 14.1.2 for details about analysis for participant 3 to 24 months of age (Cohort 3). | ERR from pre treatment to 17 to 21 days after treatment, using parasite egg counts as determined by the Kato-Katz method for Cohorts 2 and 3 and the urine filtration method for Cohort 4. Additionally, for Cohort 4b participants ERR from baseline to 35 to 40 days after treatment, using parasite egg counts as determined by the urine filtration method, | Same as Cohort 1 (Secondary analysis). | 
If the End of Study egg count is missing, it will be imputed using the Last Observation Carried Forward (LOCF) approach. Subjects with all post-baseline egg counts missing will be considered non-responders.
 
For cohort 4b, if egg counts is missing only at Extended Follow-up visit, it will be imputed by taking the value from End-of-study visit.
 |
| Secondary endpoint: cure rate as demonstrated with use of the commercially available point-of-care circulating cathodic antigen (POC-CCA®) test (Cohorts 1, 2, and 3). | | | |
| Primary (mITT) See 14.2.1 for details about analysis for participant 3 to 24 months of age (Cohort 3). | One urine sample will be collected 17 to 21 days after treatment. Cure is defined as absence of test line in the POC-CCA® test cassette (i.e., no Schistosoma antigens detected). | 
Cure rate by POC-CCA® (Cohorts 1, 2, and 3) will be analyzed in the same manner as the primary endpoint, with proportion cured and its 95% CI.
 
In addition, estimates of cure rate will be presented graphically in the form of forest plots presenting point estimates and 95% CIs of treatment groups and proportion of patients with each POC-CCA response (negative, positive 1+, positive 2+ and positive 3+) for the following time points:
 
 • D-28 to D-1 • D17 to D21 
The proportion of CCA negative, 1+, 2+ and 3+ participants (colour-coded for category) will be plotted over time, for each of the cohorts. The same will be plotted for treatment types (Biltricide® and L-PZQ), instead of cohorts.
 | 
If the End of by POC-CCA egg count is missing, it will be imputed using the Last Observation Carried Forward (LOCF) approach. Subjects with missing data will be considered non-responders.
 |
| Primary (PP) | | | No Imputation will be done. |
| 
Note:
 
 • Pooled analysis of Cohort 3 mITT population from this study and the mITT population for participants 3 to 24 months of age in the Phase II study MS200661-0005 (Cohorts 8 and 9) is detailed in Section 14.2.1. | | | |

- For mITT analysis tables will be presented with imputation and without imputation.

14.2.1 Pooled analysis of 3 to 24-month-old participants:

A total of 65 participants 3 to 24 months of age infected with *S. mansoni* is planned for analysis. Since the sample size in either the Phase II or Phase III study alone is too small to have adequate precision on the cure rate, the results in this Phase III study (MS200661-0003, Cohort 3) will be pooled with Cohorts 8 and 9 of the Phase II study (MS200661-0005, Cohorts 8 and 9). Data that will be pooled for analysis purposes comprises efficacy data, as well as demographics, other baseline characteristics and compliance & drug accountability. Relevant participants' data from the subject-level (ADSL) and efficacy ADaM datasets of the Phase II study (ADLBPARA) will be pooled with the applicable ADaM datasets from the Phase III study (to be prepared). Derived variables will be pooled, directly given that the relevant derivation rules are the same across the two studies. Imputations will be handled in the same way. Efficacy endpoint data that will be pooled from the ADLBPARA dataset from MS200661-0005 include the following:

- Infection intensity data
- Egg counts
- POC-CCA data

For presentation purposes, results from the MS200661-0003 trial will be presented in one table, and then additional tables will be prepared, specifically for participants aged 3 to 24 months, i.e. Cohort 3 from MS200661-0003, and Cohort 8 and 9 from MS200661-0005. These additional tables will be prepared for demographics, other relevant baseline characteristics and all primary and secondary efficacy results.

To align the data from MS200661-0003 the following visits from MS200661-0005 will be used in efficacy analyses:

- Baseline: DAYS -28 TO -1
- FOLLOW UP DAYS 14 to 21 (for analysis purposes this visit will be considered the same as the "DAYS 17 to 21" visit from MS200661-0003)

The definitions of analysis sets including SAF, mITT and PP are the same across the two studies, so the flag for them will not be redrived for the MS200661-0005 participants. The pooled analysis will only apply at the final analysis of the trial data.

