##### Secondary efficacy outcome: Egg reduction rate (ERR)

The WHO guideline for morbidity control of schistosomiasis (Assessing the efficacy of antihelminthic drugs against schistosomiasis and soil-transmitted helminthiases, WHO, Geneve, Switzerland, 2013) recommends measurement of group-based ERR 2 to 3 weeks after PZQ drug administration, as an appropriate parasitological indicator for morbidity control. Thus, in this study, ERRs using group-based means will be calculated for each of the cohorts. The individual ERR will also be calculated by measuring the percent reduction of egg counts for each individual.

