#### 9.4.1 Efficacy Analyses

The primary efficacy analysis will be performed on the mITT population of Cohort 1. The primary endpoint of cure rate will be calculated as the percentage of egg-positive participants at baseline who become egg-negative after treatment (as assessed by the Kato-Katz method). The exact 95% CI will be calculated based on the Clopper-Pearson method. Cohorts 2, 3, and 4 will be analyzed similarly.

The secondary endpoint of cure rate by POC-CCA® (Cohorts 1, 2, and 3) will be analyzed in the same manner as the primary endpoint, with proportion cured and its 95% CI.

The secondary endpoint of ERR will be analyzed for each of the cohorts and treatment group (Cohort 1) as group-based ERR (arithmetic and geometric) and as individual ERR (arithmetic and geometric).

Subgroup analyses will also be conducted by severity of infection (light vs. moderate/heavy infection stratification factor), country and gender. In Cohort 4, subgroup analyses will also be done by specific age groups (e.g., 3 months to 24 months of age, 2 to < 4 years of age, 4 to 6 years of age).

Sensitivity analyses may be performed on the ITT population of Cohort 1, to determine the impact of participants requiring malaria treatment, and on the PP population of Cohort 1, to assess the impact of any protocol deviations (such as completing study assessments outside the Day 17 to 21 window).

Analysis of Cohort 3 will be a pooled analysis, including the mITT population from this study and the mITT population for participants 3 to 24 months of age in the Phase II study MS200661-0005 (Cohorts 8 and 9). A logistic regression model with adjustment for study and site variability will be used to estimate cure rate.

Analysis of Cohort 4 will be performed only on the mITT population and using the same methods as for Cohort 1.

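### The bracketed formula for the geometric egg reduction rate (SAP 14.2) subtracts a log-scale count from a count-scale geometric mean and contradicts its own definition

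*SAP*

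**What the plan says.** SAP 14.2 derives the group egg reduction rate in two steps. Step 1 reads "Calculate the arithmetic group mean and geometric group mean egg counts (egp) at each visit" and defines the geometric mean as exp(mean of log(x+1)) − 1, which is back on the egg-count scale. Step 2 describes ERR_G as the "relative difference expressed in percent between the geometric mean post-treatment egg count and geometric mean pre-treatment egg count". The bracket that follows should restate this as a formula. Its first term and its denominator are the pre-treatment geometric mean, but the term subtracted is the log-"transformed post-treatment egg count".

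The protocol agrees with the words. Section 4.2.5 states that "ERRs using group-based means will be calculated for each of the cohorts", and section 9.4.1 calls for "group-based ERR (arithmetic and geometric) and as individual ERR (arithmetic and geometric"). SAP section 7 declares no change from the protocol's planned analyses, so the bracket cannot be a deliberate new measure.

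The formula reaches every group. For the three reported ERR quantities (ERR_A, ERR_G and the proportion with individual ERR of at least 90%), "95% CIs of these 3 parameters will be calculated by bootstrapping". The method entry for Cohorts 2, 3 and 4 is "Same as Cohort 1 (Secondary analysis"). For the pooled 3-to-24-month tables, SAP 14.2.1 adds: "These additional tables will be prepared for demographics, other relevant baseline characteristics and all primary and secondary efficacy results".

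**The concern.** The bracket subtracts a logarithm from a count and divides by a count. It does not say how the post-treatment logs are summarised over the group, and it does not restate the offset or the log base. It is also the only explicit computing expression for ERR_G in the plan.

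If it were coded as written, ERR_G and its bootstrap interval would be wrong in all treatment groups and in the pooled Cohort 3 tables. A log of an egg count is small beside a geometric mean count, so the result stays high even when treatment does little. Two programmers working from the same bullet could also produce different numbers, each defensible from the text.

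**Working it through.** The plan states no numerical ERR_G, so there is no figure to reproduce. The check compares the definition in words with the bracket.

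**Definitions** (natural logs, as in Step 1)
- GM = exp(mean ln(x+1)) − 1.
- Correct: 100 × (GM_pre − GM_post)/GM_pre.
- Bracket, reading A: the post-treatment term is the group mean of ln(x+1), which equals ln(1+GM_post).
- Bracket, reading B: the post-treatment term is ln(1 + arithmetic mean post-treatment count).

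**Checks with a known answer.** Every child has the same count, so A and B coincide.
- All stay at 100: correct 0%; bracket 100 × (100 − ln 101)/100 = 100 × (100 − 4.615)/100 = 95.4%.
- All stay at 24: correct 0%; bracket 100 × (24 − ln 25)/24 = 86.6%.
- All fall from 100 to 50: correct 50%; bracket 100 × (100 − ln 51)/100 = 96.1%.

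**Cohort 1 illustration**
- From the protocol: 60% light and 40% moderate/heavy infections (4.2.4); cure rates of 73.7% (70/95) and 86.3% (82/95) for group 1a (9.2, Table 5).
- Assumed: light and moderate/heavy counts of 10 and 100, or 50 and 400, eggs per gram; cure unrelated to intensity; uncured children keep their baseline count.
- Let μ = mean ln(1+baseline), G = e^μ − 1, AM = arithmetic mean baseline and p = cure rate. Then GM_post = e^((1−p)μ) − 1, correct = 1 − GM_post/G, A = 1 − (1−p)μ/G, and B = 1 − ln(1+(1−p)AM)/G.
- Mix 10/100: μ = 0.6 ln 11 + 0.4 ln 101 = 3.285, G = 25.70, AM = 46. Mix 50/400: μ = 4.757, G = 115.36, AM = 190.
- Worked case, mix 10/100 and p = 0.737: GM_post = e^(0.263 × 3.285) − 1 = 1.372. Correct = 1 − 1.372/25.70 = 94.66%. A = 1 − 0.864/25.70 = 96.64%. B = 1 − ln(1 + 0.263 × 46)/25.70 = 1 − 2.572/25.70 = 89.99%.

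| Mix | Cure | Correct | A (error) | B (error) |
|---|---|---|---|---|
| 10/100 | 73.7% | 94.66 | 96.64 (+1.98) | 89.99 (−4.67) |
| 10/100 | 86.3% | 97.79 | 98.25 (+0.46) | 92.26 (−5.52) |
| 50/400 | 73.7% | 97.84 | 98.92 (+1.08) | 96.59 (−1.25) |
| 50/400 | 86.3% | 99.20 | 99.44 (+0.23) | 97.14 (−2.06) |

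If uncured children's counts instead fall by 90%, the errors shrink to +0.06 to +0.29 points (A) and −0.7 to −1.4 points (B).

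**Cohort 4 illustration.** The 75% cure rate comes from protocol 9.2; equal baseline counts of 10 or 50 eggs/10 mL are assumed.
- G = 10: correct 91.79%, A 94.01%, B 87.47%.
- G = 50: correct 96.66%, A 98.03%, B 94.79%.

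**Bootstrap intervals** (n = 95, 70 cured, 20,000 percentile resamples, mix 10/100)
- Correct: 94.66% (91.17 to 97.05), width 5.88.
- A: 96.64% (95.23 to 97.84), width 2.61.
- B: 89.99% (87.65 to 92.36).

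In this case both wrong intervals miss the correct estimate. That does not hold throughout. With 82/95 cured, reading A's interval contains the correct value in both mixes: 97.2 to 99.1 against 97.82 (10/100), and 99.1 to 99.7 against 99.21 (50/400).

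**Weak effect.** With equal counts of 26 and 30% cured, correct ERR_G is 65.2% and A gives 91.1%. This lies well below the cure rates planned for.

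**The case against.** The strongest reply is that nobody would be misled. The same bullet gives the right definition in words, Step 1 computes the geometric mean at each visit, and the protocol says the same. The neighbouring arithmetic formula also drops a word ("mean" in its denominator), which suggests loose drafting rather than a different method. Nothing in the documents shows that the bracket was coded. This stands, and it is the main reason the point is minor.

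Step 1 also supplies a natural offset and log base, so what the bracket really lacks is the group summary. Reading A follows Step 1; reading B has little support in the text. If only A is taken seriously, the error at planned cure rates is at most about 2 points, and less than 0.3 points if uncured children's counts fall by 90%. That is a fair limit on size.

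The weak-effect example lies outside the planning range, and there the cure rate, ERR_A and the proportion with individual ERR of at least 90% would still show the failure. No hypothesis test depends on ERR_G.

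None of this removes the inconsistency. The SAP's purpose is to give detailed technical specifications, and this one returns 95.4% when nothing has changed. The modification history records that the ERR derivation was updated in version 2.0, yet the bracket stands in the current text.

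**Conclusion.** The concern holds, as a minor point. The bracketed ERR_G formula is wrong as written and conflicts with its own verbal definition, with Step 1 and with the protocol. This does not depend on any assumed data.

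The size does depend on assumptions, because the documents give no baseline counts. For Cohort 1 at planned cure rates, with the assumed baselines and uncured children unchanged, literal coding would shift ERR_G by +0.2 to +2.0 points (A) or −1.25 to −5.5 points (B). For Cohort 4 at 75% cure the shift is +2.2 to +1.4 points (A) or −4.3 to −1.9 points (B), for geometric means of 10 to 50. It would also distort the interval: under A at 70/95 cured and a baseline geometric mean of 25.7, the interval is less than half its proper width. Large point errors arise only when the treatment effect is weak.

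The primary cure rate and the individual ERR are unaffected. The ERR_A denominator needs only an editorial correction.

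**What to change.** Replace the bracket with ERR_G = 100 × (GM_pre − GM_post)/GM_pre, stating that both geometric means are those of Step 1, exp(mean log(x+1)) − 1. Confirm that the analysis and bootstrap programs use this form in all treatment groups and in the pooled Cohort 3 tables; a test dataset in which no count changes should return 0%. In the same edit, add "mean" to the ERR_A denominator.

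The cost is one formula, one word and one programming check. It needs no extra data and has no drawback.
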